5.4 Participant Adherence Monitoring

Empty pill containers will be returned to site investigator at the conclusion of each 2-week period during the dose escalation phase, and at 16 weeks and the end of the study during the treatment phase. Pill counts will be performed to assess participant adherence with prescribed study medications.

5.5 Prior and Concomitant Therapy

Baseline medication use (both oral and intravenous) and history of prior coronary revascularization procedures will be collected at baseline. A participant's standard of care medication may be changed prior to study participation if considered clinically appropriate. No changes in drug dose or medications will be made without the approval of the prescribing physician. Concomitant medical therapies and coronary revascularizations will be collected throughout the course of the study. Use of sildenafil, vardenafil or tadalafil is listed as an exclusion criterion. Participants requiring the initiation of therapy with these agents during the study will have study medications withdrawn, but will continue to be followed for adverse events and efficacy assessments. No other concomitant therapies are prohibited.

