4.2 Exclusion Criteria

- a) Serum potassium ≥ 6.5 mEq/L within 2 months prior to screening
- b) Unscheduled dialysis for hyperkalemia within the 3 months prior to screening
- c) Pre-dialysis hypotension defined as pre-dialysis SBP <100 mm Hg (seated measurement) within 4 weeks prior to the screening visit
- d) Recurrent intra-dialytic hypotension defined as either of the following:
 - o systolic blood pressure <80 mm Hg during ≥ 3 dialysis sessions in the 30 days prior to the screening visit, or
 - o treatment for hypotension or symptoms of hypotension during ≥ 3 dialysis sessions in the 30 days prior to the screening visit. For this criterion, hypotension is defined as systolic blood pressure <100 mm Hg.
- e) Mitral valve repair or replacement
- f) Severe mitral valve disease by echocardiography, coronary angiography or cardiac magnetic resonance imaging
- g) Anticipated kidney transplant, change to peritoneal dialysis, or transfer to another dialysis unit within 6 months
- h) Expected survival <6 months
- i) Allergy to study medications (ISD, HY, adenosine or dipyridamole)
- j) Active use of sildenafil, vardenafil or tadalafil
- k) Current severe aortic stenosis or other cause of LV outflow obstruction
- l) Pregnancy, anticipated pregnancy, or breastfeeding, confirmed by serum pregnancy test on the day of PET scan
- m) Incarceration
- n) Participation in another intervention study
- o) Use of monoamine oxidase inhibitors
- p) Contraindication to adenosine including

- 2nd or 3rd degree heart block, sick sinus syndrome or symptomatic bradycardia (without a functioning pacemaker)
- moderate or severe asthma
- chronic obstructive pulmonary disease

q) Active use of any of the study medications unless participant and physician willing to discontinue prior to enrollment.

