4.4 Early Withdrawal of Participants

4.4.1 When and How to Withdraw Participants

Early withdrawals will be discouraged and participants who are not willing to continue the intervention will be encouraged to remain in the study and continue study evaluations. However, participants may be withdrawn from the study under the following circumstances that have the potential to compromise patient autonomy or safety:

- a) Pregnancy
- b) Withdrawal of consent
- c) Allergy to or documented intolerance of study medications (e.g. recurrent hypotension on the lowest dose of study medications)
- d) Non-compliance with dialysis schedule compromising ability to follow serum potassium on a monthly basis
- e) Organ transplantation
- f) Change to a different dialysis modality

- g) Initiation of sildenafil, vardenafil or tadalafil therapy
- h) Transfer to non-participating dialysis unit

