6.7 Hypotension Procedures

In the event of recurrent intra-dialytic hypotension or serious hypotension not attributable to acute events (e.g. acute myocardial infarction, sepsis), the investigator will review the participant's non-study anti-hypertensive medications, dry weight, and volume status. The participant's clinician will be contacted to consider the following interventions listed in the preferred order of implementation:

- 1) Decrease non-study anti-hypertensive medication(s)
- 2) Increase dry weight if there is no evidence of peripheral or pulmonary edema
- 3) Reduce ultrafiltration rate by increasing dialysis session duration
- 4) Reduce dose of study medication if:
 - a. Peripheral or pulmonary edema is present
AND
 - b. There are no other anti-hypertensive medications prescribed OR other anti-hypertensive medications should not be discontinued (e.g., beta blocker following myocardial infarction)
- 5) Discontinue study medication when reduction below minimal dose is required

Treating clinicians will be free to manage hypotension according to standard clinical practices and are not obligated to follow the study guidelines with respect to non-study medication, fluid removal rate, or dry weight. In contrast, dose reduction or discontinuation of study drug will be directly managed by study staff in accordance with the guideline. All enrolled participants will continue to be followed for the occurrence of adverse events and for end of study cardiac testing regardless of whether study medications are discontinued.

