7.3 Intent-to-treat Analysis and Missing Data

An intent-to-treat analysis, in which all available data on all randomized participants are included, will be used for the primary comparison of treatments. All attempts will be made to keep missing data to a minimum, and participants who withdraw from treatment will be encouraged to continue on study in order to provide complete follow-up information. Thus, irrespective of withdrawal from treatment, all participants should continue to be followed with all scheduled outcome evaluations until the end of the study. However, it is expected that up to 10% of the randomized participants may withdraw prior to the final assessment of response at 26 weeks. These participants will be included in the denominator for evaluation of the response rates defined for the primary endpoint.

The characteristics at the time of randomization for those participants without complete follow-up will be examined; however, there will be limited statistical power to detect any but major differences between these participants and those with complete follow-up. In addition, in order to assess the potential biases introduced by differential withdrawal among treatment arms, a comparison of withdrawal rates and/or time to withdrawal will be included as an ancillary analysis to the primary endpoint comparison.

Secondary analyses will examine the all-treated, as-treated, and per-protocol populations as defined below. Given the pilot nature of this study and small sample size, no corrections will be made for

multiplicity in these additional analyses. The possibility of false-positive results is acknowledged and results of these analyses will be considered strictly exploratory.

Nevertheless, these secondary analyses may provide important, hypothesis-forming insights into mechanism of action and optimal design for further studies in the event that significant deviations from the protocol or dropout from the study are felt to have had an important impact on the results.

The analysis populations are defined as follows:

- All-randomized / intention-to-treat (ITT) population: Any participant randomized into the study, regardless of whether study drug was received.

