- As-treated population: The as-treated population is the same as the ITT population (i.e., any participant randomized into the study regardless of whether study drug was received). However, for the as-treated analysis, patients in the active drug group who did not receive at least one dose of study drug will be classified into the placebo arm.
- All-treated population: Any participant randomized into the study who received at least one dose of study drug.
- Per-protocol population: Any participant who was appropriately randomized, and received the protocol-dictated study drug exposure ($\geq 75\%$ of prescribed doses) and endpoint assessments through 24 ± 2 weeks.

Because dose-related efficacy and safety are important questions of interest in this study, the ITT analysis will be supplemented with an analysis of the as-treated population. Although ITT approaches provide the least-biased analysis of treatment efficacy and safety, as-treated analyses provide important complementary information on biological effectiveness of therapy (e.g. theoretical efficacy if drug were tolerated by all participants) and on the effects of actual doses used that is not captured by (ITT) analyses in which the unit of analysis is a randomized therapy that may not have been used by individual participants¹⁴⁹. For this reason, as-treated approaches provide important complementary information to ITT analyses and are typically mandated as an important secondary analyses of clinical trials by the FDA¹⁴⁹. Given a treatment protocol that allows for dose reduction of study medications, the as-treated analysis will provide critical information in this trial for assessing dose-related efficacy and the incidence of adverse events such as hypotension. As-treated analyses will assign treatment dose according to the dose used at the time of an adverse event (safety analyses) or according to the mean dose received during the trial (efficacy analysis).

In general, missing data will not be imputed. Every effort will be made to use statistical methods that are robust to missingness, and the number of participants included with each analysis will be given with the results.

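### After randomisation nothing limits open-label isosorbide dinitrate or hydralazine in either arm, and the per-protocol set would not remove placebo participants who take it

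*Combined protocol and SAP*

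**What the plan says.** **At entry.** Section 4.2(q) excludes "Active use of any of the study medications unless participant and physician willing to discontinue prior to enrollment". Section 4.3 adds that the treating nephrologist is contacted about suitability before enrolment.

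**After randomisation.** Section 5.5 has concomitant therapies recorded throughout. It withdraws study drug if sildenafil, vardenafil or tadalafil becomes necessary, and ends: "No other concomitant therapies are prohibited". The only drug-initiation item in the withdrawal list of 4.4.1 is "Initiation of sildenafil, vardenafil or tadalafil therapy".

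**Hypotension.** Section 6.7 puts reduction of non-study antihypertensives first among its suggested steps. It then says "Treating clinicians will be free to manage hypotension according to standard clinical practices and are not obligated to follow the study guidelines" as regards non-study medication, fluid removal and dry weight. Study-drug reductions stay with study staff.

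**Imaging.** Section 6.9.2 has vasoactive drugs, with nitrates named, withheld for 24 hours before PET. HY is not named. Section 6.9.1 states no such hold for the echocardiogram.

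**Analysis sets (7.3).** The per-protocol set is "Any participant who was appropriately randomized, and received the protocol-dictated study drug exposure" (at least 75% of prescribed doses), with endpoint assessments completed. As-treated reclassification runs one way only: "patients in the active drug group who did not receive at least one dose of study drug will be classified into the placebo arm". As-treated dose is the dose in use at an adverse event or, for efficacy, the mean dose over the trial. Of the secondary populations the plan says that "results of these analyses will be considered strictly exploratory".

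**The concern.** Criterion (q) serves to start both arms free of the drugs under test. Nothing carries that purpose past randomisation, and the closing sentence of 5.5 is an express permission rather than silence. A participant who stopped HY in order to enrol could be put back on it at any time.

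Two things are at stake.

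- **Placebo arm.** Section 7.1 says the trial's product is estimates of change, with their standard deviations, for designing later studies. Open-label ISD or HY on placebo pulls the arms together. The per-protocol analysis, where one would look for a cleaner contrast, would still contain these participants.
- **Active arm.** Open-label drug would come on top of a target of 120 mg/day ISD and 225 mg/day HY, in patients for whom section 1.4 already names hypotension during dialysis as a risk.

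**Working it through.** **1. The rules side by side**

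| Rule | Response to open-label ISD or HY |
|---|---|
| 4.2(q) | Applies at entry only |
| 5.5 | Recorded, not restricted |
| 4.4.1 | Not listed |
| 6.7 | Non-study antihypertensives are the first to be reduced, but only after recurrent or serious hypotension, and not binding on treating clinicians |
| 6.9.2 | Nitrates withheld for 24 hours before PET; HY not named |
| 7.3 per-protocol | None: depends on randomisation, study-drug doses and endpoint assessments |
| 7.3 arm reclassification | None: moves participants only from active to placebo |
| 7.3 as-treated dose | Unclear whether non-study drug counts |

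**2. The plan's own figure**

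Inputs from 7.1: 8 per arm; CFR difference 0.75 with SD 0.5; E' difference 3.0 cm/s with SD 2.0 cm/s; P<0.05, taken as two-sided. Both are standardised differences of 1.5 (0.75/0.5 and 3.0/2.0). A two-sample t-test gives power 0.797, so the stated 80% reproduces.

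**3. Dilution from use in the placebo arm**

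The documents give neither a restart rate nor the effect of one agent alone, so both are varied. Let k be the number of affected placebo participants of 8, and f the share of the full combination effect that each gains, from 0 to 1. Section 1.1 expects the combination to do more than ISD alone, so f = 1 is an upper bound.

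Expected difference = D × (1 − f·k/8)

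| | CFR, f = 0 | CFR, f = 1 | E', f = 0 (cm/s) | E', f = 1 (cm/s) |
|---|---|---|---|---|
| k = 1 | 0.75 | 0.75 × 7/8 = 0.656 | 3.0 | 3.0 × 7/8 = 2.625 |
| k = 2 | 0.75 | 0.75 × 6/8 = 0.563 | 3.0 | 3.0 × 6/8 = 2.25 |

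The largest loss is therefore 1/8 = 12.5% of the contrast per affected participant.

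**4. Size against the planned precision**

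95% half-width = t(14) × SD × √(2/8), with t(14) = 2.145.

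- CFR: 2.145 × 0.5 × 0.5 = 0.536
- E': 2.145 × 2.0 × 0.5 = 2.145 cm/s

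Largest shift divided by half-width:

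- k = 1: 0.094/0.536 = 0.175 for CFR; 0.375/2.145 = 0.175 for E'
- k = 2: 0.188/0.536 = 0.350 for CFR; 0.75/2.145 = 0.350 for E'

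Even at the ceiling, the shift is well inside the sampling error of a trial this size.

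**5. Active arm**

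Full study dose is 40 × 3 = 120 mg/day ISD and 75 × 3 = 225 mg/day HY, and open-label drug adds to this. The documents give no dose-response, so neither the extra hypotension nor any effect on the efficacy contrast can be sized. Active-arm use could partly offset placebo-arm dilution.

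**The case against.** The case for leaving the text alone is respectable. The primary analysis is intention-to-treat, and letting background therapy run is a legitimate treatment-policy choice. The sets that fail to respond are exploratory. Concomitant drugs are recorded, so open-label use can be tabulated afterwards. The 24-hour hold before PET limits any acute nitrate effect on CFR. The ceiling in the working needs a placebo participant to gain the whole 26-week combination effect, which a mid-trial restart of one agent would hardly give.

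Most of this stands, and it limits the size of the point. It does not close the gap. Recording detects use but triggers nothing. The PET hold does not remove sustained exposure, and the hypotheses in 1.1 concern fibrosis and microvascular loss. The E' measurement has no hold at all.

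Several stronger readings are tempting, and the documents do not support them:

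- *That 5.5 contradicts 4.2(q).* It does not: (q) is an entry rule. Section 5.5 undercuts its purpose.
- *That open-label use will be common.* Section 1.4 says HY is routine in dialysis patients generally. That is not a restart rate for people whose physician agreed to stop it.
- *That the phosphodiesterase-inhibitor rule shows ISD and HY were overlooked.* That rule answers a drug interaction (1.4), not contamination.
- *That the as-treated analysis ignores non-study drug.* Section 7.3 speaks of doses actually used, while its context is reduction of study medication. The wording is ambiguous and needs only clarifying.
- *That study drug should be held or reduced whenever open-label ISD or HY is given.* This would remove no contamination on placebo and would take assigned therapy from active participants who stay in the intention-to-treat analysis. It would also cut across the conditions in 6.7, and the plan has no procedure for re-escalating afterwards.

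**Conclusion.** The point holds as a gap worth closing because closing it is cheap. Open-label ISD or HY is permitted in either arm after randomisation, and the per-protocol set does not respond to it. The effect on the E' and CFR contrasts runs from zero to at most 12.5% per affected placebo participant. This assumes all 8 contribute data and that open-label use does no more than the full study combination. One such participant shifts the estimate by at most 17.5% of the 95% half-width, and two by at most 35%. In the active arm the concern is added dose and hypotension, which cannot be sized from the documents.

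A reader might infer that the primary comparison is invalid or the sample size wrong. Neither follows. Intention-to-treat still estimates the effect of assignment under whatever background therapy occurs, and the stated power reproduces.

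**What to change.** **Section 5.5.** Put this before the last sentence, which then follows unchanged ("No other concomitant therapies are prohibited"):

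> From randomisation through the Week 26 assessments, non-study ISD and HY are not to be started or restarted unless clinically necessary with no suitable alternative; the investigator is to be informed. Such participants continue follow-up, have the Week 26 echocardiogram and PET, and remain in the ITT analysis.

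Leave study-drug dose changes to 6.7. Do not add an automatic hold or reduction.

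**Section 7.3.** Add:

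> Use of non-study ISD or HY after randomisation is a per-protocol deviation and is reported by arm (agent, dose, dates).

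As a minor clarification, state that as-treated dose includes non-study ISD and HY.

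**Cost.** Wording, plus coding of concomitant-medication data already collected; no new visits or tests. Clinicians lose a little freedom in choice of agent, and the per-protocol set may shrink. Removing open-label users from that set selects on a post-randomisation event, so the analysis must stay exploratory, as 7.3 already labels it.

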5.6 Packaging

Study drug will be distributed in participant-specific containers. Labeling will include patient ID, protocol number, study-center, expiration date, instructions, and "prescribing" physician (study investigator).

5.7 Blinding of Study Drug

Generic ISD, HY will be purchased, and matching placebos will be prepared by the IDS. The identity of matched placebos will be concealed from both investigator and participants. Only the IDS will remain unblinded. See Section 8.4 for further information on un-blinding procedures, if needed.

5.8 Receiving, Storage, Dispensing and Return

5.8.1 Receipt of Drug Supplies

The IDS pharmacist will distribute study agent to the participant during their study visits. Alternatively, investigator may deliver drug supply to the patients during the study visits.

General Study Product Accountability, Patient Specific Study Product Accountability, and if necessary, Shipment Tracking Accountability Logs will be created by the IDS staff and study product use documented on respective logs. Documentation includes study product receipt, storage, dispensing, and final disposition. Study product must be inventoried at least once per month within 30 days of the count for the previous month.

5.8.2 Storage

ISD, HY, and matched placebo should be stored at <25°C. Study supplies will be stored in the IDS pharmacy until the date of distribution to study participants.

5.8.3 Dispensing of Study Drug

The pharmacist or trained site designee will dispense study drug to the patient and complete a dispensing/accountability log for each participant. Documentation of training will be held in the site's regulatory binder.

5.8.4 Return or Destruction of Study Drug

Medication containers will be returned by patients at the end of each 2-week or 90-day period and remaining pills counted to assess adherence. Unused supplies of study drug will be destroyed by study staff once the pill count is completed and documented.

6 Study Procedures

Study procedures and testing are provided in the visit schedule in **Section 15**. Medical history (hypertension, coronary artery disease, coronary revascularization, diabetes, hypercholesterolemia, cerebral or peripheral vascular disease, peptic ulcer disease, cancer, smoking, arrhythmia, cause of ESRD, dialysis vintage, prior transplant), baseline medications, dialysis unit labs (chemistries, PTH, complete blood count), vital signs, and dialysis prescription will be collected at baseline.

6.1 Pre-screening Visit

Dialysis unit records and study center medical records will be reviewed to assess eligibility. The treating nephrologist for potentially eligible patients will be contacted to further assess eligibility and obtain permission to contact the patient. Patients remaining eligible after this assessment will be approached in person at the dialysis unit to confirm eligibility for and interest in participation. Participants signing IRB-approved informational flyers which expressly provide consent to be called, may be screened by telephone. Participants will be provided with a copy of study brochures and the consent form to review at their leisure, and they will be provided with study staff contact information so that they can reach the investigator or a designee with additional questions about the study.

6.2 Screening Visit

Eligible participants expressing interest in participation will be scheduled for a screening visit. This visit may take place at the local dialysis unit or at the study center. Informed consent will be obtained and documented, eligibility criteria will be confirmed, and the baseline visit will be scheduled during this

visit. Demographic data (age, sex, race), vital signs, edema assessment, medication use, dialysis labs, and medical history will be obtained following informed consent.

6.3 Baseline Visit/Randomization Visit

The baseline visit will be scheduled within 4 weeks of the screening visit. A physical examination will be conducted. Data on medication use, baseline medical conditions, vital signs and edema assessment will be collected. Dialysis prescription, dialysis labs, medications, and vital signs will be updated within 3 days prior to the baseline visit. Serum and plasma will be collected, aliquoted and frozen at -80°C. Additional blood will be drawn for testing of baseline chemistries and blood counts as well as local lab serum pregnancy testing (in pre-menopausal women). Baseline TDI echo and PET scans will be performed. The echo and PET scans are not required to occur on the same day, however, they both should be completed prior to randomization and drug distribution. If LVEF stratification needs to be determined from the baseline echo, then there may be up to a 72-hour delay between the baseline visit and randomization in order to allow for a limited reading of the study TDI echo. A clinical echocardiogram will be used for LVEF determination if available within 6 months of the baseline visit date. Once all the baseline activities have been completed, the patient will be randomized and a 1-week + 3 day supply of study medication will be dispensed. The baseline/randomization visit can be scheduled over two dates within a 10-day window.

